8.3.3 CLASSIFICATION OF AN ADVERSE EVENT

8.3.3.1 SEVERITY OF EVENT

Not applicable.

8.3.3.2 RELATIONSHIP TO STUDY INTERVENTION

Not applicable.

8.3.3.3 EXPECTEDNESS

There are no known expected adverse reactions. SPIRIT has been tested in 5 RCTs with various patient populations with serious chronic conditions and in 3 different regions and settings. Although possible adverse reactions to the intervention may include fatigue or emotional distress during the intervention session, no such reactions have been observed in the previous studies. Thus, these reactions are very unlikely to occur and will be considered “unexpected.” Intervention sessions will stop if any of these events occurs.

8.3.4 TIME PERIOD AND FREQUENCY FOR EVENT ASSESSMENT AND FOLLOW-UP

Not applicable.

8.3.5 ADVERSE EVENT REPORTING

The possible adverse reactions (fatigue, emotional distress during the intervention session), if ever occurs, will be tracked (documented in the study REDCap) and the aggregated numbers will be reported at the upcoming biannual DSMB meeting.

Any disease-related events (DREs) common in the study population (e.g., expected) such as death will not be reported per the standard process of reporting but will be monitored so that surrogates’ post-bereavement outcomes and end-of-life treatment intensity data (Medicare claims data) can be collected timely. However, any participant’s death will be reported to IRB through annual progress report and included in the NIH annual progress report.

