2.3 RISK/BENEFIT ASSESSMENT

2.3.1 KNOWN POTENTIAL RISKS

As the SPIRIT intervention has proven to be safe and efficacious, this Phase III pragmatic trial involves very minimal or low risk. Patient and surrogate participants may experience an emotional reaction (e.g., anxiety) or fatigue during the intervention or data collection. In our previous studies,¹⁷⁻²⁰ intervention dyads were less apprehensive and more satisfied with the quality of communication than control dyads. It is expected that psychological burden caused by the SPIRIT intervention will be less than or equal to that of usual care.

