Examine the effectiveness of SPIRIT and usual care on EOL treatment intensity	Health care utilization (percentages of patients hospitalized, having ICU admission, and having intensive procedures, and LOS)	To examine whether SPIRIT reduces aggressive EOL treatment
Supplement		
Estimate the effects of the SPIRIT-dementia intervention on the preparedness outcomes and care decisions	Dyad congruence on goals of care (binary); Patient decisional conflict (scale); Surrogate decision-making confidence (scale) Composite outcome (goals-of-care congruence with confident surrogate; binary) Care decisions (withdrawal from dialysis, Do-Not-Resuscitate order, hospice enrollment)	The primary goal of SPIRIT is to prepare the patient and surrogate for end-of-life decision making. The preparedness outcomes will indicate whether or to what extent SPIRIT accomplished the goal. Care decisions will reflect the effects of SPIRIT on end-of-life decision making.
Estimate the effects of the SPIRIT-dementia intervention on surrogates' post-bereavement distress	Anxiety symptom score (HAS-anxiety); Depression symptom score (HAS-depression)	Surrogate prepared by SPIRIT for EOL decision making should experience less post-bereavement distress.
Supplement cohort study (non-clinical trial)		
Assess the effect of the pandemic on the stability of end-of-life care preferences and on our key outcomes (dyad congruence on goals of care, patient decisional conflict, and surrogate decision-making confidence).		

Measurement and data collection time points

Outcome	Measure	Completed by			Time points
		pt	srgt	prov	
Effectiveness outcome evaluation					
Preparedness					
Dyad congruence	Goals-of-Care Tool (2 end-of-life scenarios)	✓	✓		Baseline and 2 wks
Patient decisional conflict	Decisional Conflict Scale (range, 1-5)	✓			Baseline and 2 wks
Surrogate decision-making confidence	Decision Making Confidence Scale (range, 0-4)		✓		Baseline and 2 wks
Overall preparedness	Preparedness for End-of-Life Decision Making (range, 26-104)	✓	✓		Baseline and 2 wks
Post-bereavement distress	HADS (each subscale range, 0-21) PTSS-10 (range, 10-70)		✓		Baseline and 3 mo. after patient death
End-of-life care intensity	Percentages of patients hospitalized, having ICU admission, and having intensive procedures and length of hospital stay				Medicare claims data after patient death
Initial implementation process evaluation					

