8.2 SAFETY AND OTHER ASSESSMENTS

SPIRIT is a one-time psychoeducational intervention. The study involves very low risk and the potential risk may include fatigue or emotional upset during the session.

Fatigue

As part of outcome assessment, HADS and PTSS-10 will be completed. Although these measures are not diagnostic tools, if a surrogate's HADS-Depression is high (≥ 15), the data collector will ask the surrogate if she/he is aware of the mood state and encourage to speak to his/her primary care provider. If a surrogate expresses suicidal ideation, the data collector will immediately notify the local site coordinator who will confer with the Site PI. This Site PI will determine if referral to the local mental health clinic (during hours) or the 24-hour Emergency Psychiatry Service (after hours) for evaluation of mental health or emergency intervention is necessary.

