10.1.6 SAFETY OVERSIGHT

Safety oversight will be under the direction of a Data and Safety Monitoring Board (DSMB) composed of 5 individuals with the appropriate expertise, including dialysis care, advance care planning, palliative care, clinical trials, intervention testing, and biostatistics. Members of the DSMB are independent from the study conduct and free of conflict of interest (see signed disclosure forms).

The DSMB will meet bi-annually to evaluate the study progress, including assessment of data quality, timeliness, participant recruitment, rates of eligibility and ineligibility across study clinics and sites/states, accrual and retention, participant risk versus benefit, performance of trial sites, patient deaths, and any adverse events or care providers' concerns that can affect study outcome. Consistent with prior end-of-life communication interventions, including our prior trials, we do not expect that the intervention will alter mortality rates. Nonetheless, this will be one of the measures monitored by the DSMB. The DSMB will compare recruitment rate and sample characteristics to assumptions used for power calculations. The DSMB will monitor the design factor, intra-cluster correlation coefficient, to assess whether the study will have expected power. Formal interim analyses are not planned for several reasons: (a) the SPIRIT efficacy has been established, (b) risks associated with SPIRIT are very minimal, (c) the control condition is usual care, not a placebo, and (d) the proposed study also aims to gather implementation data, including sustainability, that are critical for widespread implementation. Finally, the DSMB will not monitor fidelity/adherence data and make recommendations for ways to improve adherence because of the pragmatic nature of the proposed trial (i.e., seeking real world answers). The DSMB will operate under the rules of an approved charter that will be written and reviewed at the organizational meeting of the DSMB.

See DSMB Charter.

For Supplement Aims:

Although the proposed study involves minimal risk, we will implement a data and safety monitoring plan at multiple levels to ensure the safety of participants and the validity and integrity of the data:

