10.1.8 QUALITY ASSURANCE AND QUALITY CONTROL

We will use centralized training of research staff for recruitment and data collection activities as appropriate. The PI and Project Director will train staff in all study procedures. All project staff will complete university sponsored research integrity training, including modules on the protection of human subjects, HIPAA, and Good Clinical Practice. All roles, responsibilities, and a protocol with scripted subject contacts will be clearly delineated in the study Standard Operating Procedures (SOPs). These SOPs will be accessible via REDCap.

Data collectors/recruiters will attend a competency based, one-day training session that the PI and Project Director will convene. Following a demonstration by the PI or Project Director on how to recruit participants and obtain informed consent, the recruiters will be expected to perform three satisfactory practice recruitment sessions before actual performance. The final practice sessions will be audio- or video-recorded and reviewed for adherence to the protocol. After demonstrating satisfactory performance of consenting sessions, the recruiters will be authorized to recruit and enroll participants.

Training for data collection will include scripted data collection techniques with special attention to assessing participant fatigue or discomfort during the data collection session. Data collectors will conduct a series of three practice baseline and follow-up data collections using volunteers. After demonstrating satisfactory performance on data collection, they will be authorized to perform data collection activities with enrolled participants. They will also need to demonstrate completeness of data collection activities using REDCap.

Each study site will perform internal quality management of study conduct, data collection, documentation and completion. In general the following strategies will be employed:

- Use of data collection and data entry SOP
- Before ending the data collection session, review the data entry form in REDCap for any missing data
- Each data collector signs his/her work
- Audit research staff members' performance (e.g., consenting and data collection) Biannually.

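### Fatigue and emotional distress are tracked for the DSMB only during the SPIRIT session, so the control arm cannot contribute to the tracked counts, although the protocol names the same risk at data collection

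*Combined protocol and SAP*

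**What the plan says.** Section 2.3.1 (Known Potential Risks) gives the risk for both members of the dyad and at two kinds of contact: "Patient and surrogate participants may experience an emotional reaction (e.g., anxiety) or fatigue during the intervention or data collection". It then states an expectation that "psychological burden caused by the SPIRIT intervention will be less than or equal to that of usual care", and 2.3.3 repeats it.

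The safety sections are narrower. Sections 8.2, 8.3.1 and 8.3.3.3 speak only of fatigue or distress in the session. Section 8.3.5 sets the recording rule in the same terms: "The possible adverse reactions (fatigue, emotional distress during the intervention session), if ever occurs, will be tracked". The records go into REDCap and "the aggregated numbers will be reported at the upcoming biannual DSMB meeting". No split by arm is mentioned. Section 8.3.4 (time period and frequency of event assessment) and section 9.4.4 (safety analyses) are both marked as not applicable.

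Section 10.1.6 asks the DSMB to weigh "participant risk versus benefit" and gives it a general remit over adverse events and care providers' concerns. Section 10.1.8 trains data collectors with "special attention to assessing participant fatigue or discomfort during the data collection session". Section 8.2 adds a referral pathway for surrogates with HADS-Depression of 15 or more, and for suicidal ideation: "If a surrogate expresses suicidal ideation, the data collector will immediately notify the local site coordinator", who confers with the site PI. Section 10.1.7 has REDCap flag the high HADS score. The measurement table in section 3 gives HADS and PTSS-10 to surrogates only, at "Baseline and 3 mo. after patient death".

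**The concern.** A risk named for two settings is recorded in only one of them, and that setting exists in only one arm. The tracked reactions can then be counted under SPIRIT but not under usual care. A one-arm count cannot inform a comparative statement. Any nonzero count in the SPIRIT arm has no background rate beside it, and a zero in the control arm says nothing about control participants.

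Two consequences follow. The DSMB is asked to weigh risk against benefit without systematic comparative data on the only harms the protocol considers plausible. The final report will also have no planned harms table by arm, because 9.4.4 asks for none. The most serious psychological signals the protocol prepares for, the high depression score and suicidal ideation, are handled as care matters, with no stated rule that they also be counted.

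**Working it through.** The plan states no figure on this point, so there is none to reproduce. The check compares the texts first and then gives the size.

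**1. Which reactions have a recording route?**

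- In the session, SPIRIT arm: yes (8.3.5, REDCap, then the DSMB).
- In the session, control arm: no such session exists during participation. Section 4.1 places delayed SPIRIT in Year 4. Section 8.1 says that the delayed phase evaluates care providers only, because patients and surrogates have by then finished.
- At data collection, either arm: named as a risk (2.3.1) and looked for by trained staff (10.1.8), but no recording or reporting step is given.

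**2. Does another channel fill the gap systematically?**

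- Unanticipated problems (8.4.2): reporting requires a relation to the intervention.
- Acceptability questionnaire (8.1): it covers comfort and satisfaction, but about SPIRIT sessions, so it gives no control comparison.
- HADS flags and suicidal ideation (8.2, 10.1.7): these arise in both arms, in surrogates, and lead to referral. No route to the DSMB is stated.
- HADS and PTSS-10 scores: none is taken at 2 weeks. A surrogate whose patient survives has no score after baseline. With 400 surrogates the number is 400 × (1 − proportion of patients dying). At the 40% deaths in 8.1 this is 400 × 0.60 = 240; at the 20% in 4.1 it is 400 × 0.80 = 320. Deaths during the extended follow-up would lower both figures.
- DSMB and investigator meetings (10.1.6, 10.1.8): they can take up any adverse event, but no collection rule feeds them beyond 8.3.5.

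**3. Size under the present rule.** Control reactions that the rule can record: 0, at any true rate. Assume 200 control dyads (equal allocation, not stated for dyads) and a true per-dyad reaction rate at calls of 2%, 5% or 10% (the documents give no rate). Reactions occurring are 200 × 0.02 = 4, 200 × 0.05 = 10 and 200 × 0.10 = 20. Tracked: 0 in each case.

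**4. What two-arm recording would give.** Inputs: 200 dyads per arm (assumed); ICC 0.01 to 0.04, the range in 9.2 for the trial's outcomes, assumed to apply here; 19 clusters (power table, 9.2) or 28 (4 + 3 + 8 + 5 + 8, section 6.3).

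- Dyads per cluster m: 400/19 = 21.05, or 400/28 = 14.29.
- Design effect 1 + (m − 1) × ICC: smallest 1 + 13.29 × 0.01 = 1.13; largest 1 + 20.05 × 0.04 = 1.80.
- Effective n per arm: 200/1.133 = 176.5 down to 200/1.802 = 111.0.
- 95% CI half-width for the difference, 1.96 × √(2p(1 − p)/n). At p = 0.05: 1.96 × √(0.095/176.5) = 0.046 to 1.96 × √(0.095/111.0) = 0.057. The same formula gives 0.029 to 0.037 at p = 0.02 and 0.063 to 0.079 at p = 0.10.
- With 80% power (two-sided 5%), a 5% control rate could be told from about 14% to 17%.

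So the data would be descriptive, enough to show a large difference but not a small one.

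**The case against.** The best defence is one of scope. Section 8.3.5 follows 8.3.3.3, which speaks of reactions to the intervention, and by that definition a control dyad cannot have one. SPIRIT is about an hour of structured conversation, and 8.3.3.3 reports no such reactions in previous studies. An independent DSMB also sees deaths and may take up any adverse event. This stands as an argument for a light remedy. It does not explain why 2.3.1 names data collection as a source of the same risk and the recording rule then leaves it out.

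Several stronger readings are tempting, and the documents do not support them:

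- *That nothing from the control arm can reach the DSMB.* Section 10.1.6 leaves an ad hoc route and deaths are monitored. The zero applies only to the tracked fatigue and distress reactions.
- *That harms rest solely on the interventionist's own report.* Section 8.3.5 does not say who reports. Section 6.4 has the provider document each encounter, but a research assistant also asks patients and surrogates about the sessions at 2 weeks.
- *That a suicidal-ideation report stops with the site PI.* The text states no further step, which is not the same as ruling one out. The DSMB charter, SOPs and manual of procedures are cited but are not available here.
- *That the trial sets out to prove equal or lower burden.* The statement is an expectation, and 9.1 contains no safety hypothesis. Post-bereavement HADS and PTSS-10, and patient decisional conflict at 2 weeks, are compared between arms and give partial evidence on psychological effect.
- *That hardly any surrogate will ever be reassessed.* The amendment history reports deaths below 4%, but as a snapshot during follow-up and as the reason for requesting 12 more months. It is not an end-of-trial rate.

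Two practical objections also stand in part. Fatigue in dialysis patients will often reflect illness, and questions about distress could lead a participant to mention SPIRIT to a blinded assessor.

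**Conclusion.** The point holds in a limited form. The recording rule in 8.3.5 is narrower than the risk in 2.3.1. Followed as written, it gives one-arm ascertainment of fatigue and emotional distress. The DSMB then lacks systematic between-arm data on the expected burden, and the high-depression flags and suicidal-ideation reports have no stated route to it.

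The firm figure is zero trackable control-arm reactions at any true rate. The 4, 10 or 20 missed reactions rest on assumed rates and an assumed 200 control dyads. No primary or secondary inference changes. This is a gap in harms reporting that should be closed because the remedy is small, not evidence that participants are unsafe. It concerns the parent trial. The dementia supplement has its own monitoring committee text in 10.1.6.

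**What to change.** 1. In 8.3.5, align the rule with 2.3.1: record fatigue and emotional distress at the existing baseline and 2-week calls, for patients and surrogates in both arms. Use neutrally worded items placed after the outcome measures, so that any disclosure of allocation comes after those measures are complete.
2. Log each HADS-Depression flag (15 or more) and each suicidal-ideation report as a tracked event, with the arm and the assessment at which it arose. The care pathway in 8.2 and 10.1.7 stays as it is.
3. Report counts by arm at the biannual DSMB meetings already planned. Use the 2-week call for the between-arm comparison, show baseline as background, and list session events separately because only one arm has sessions.
4. Replace the not-applicable entry in 9.4.4 with this descriptive tabulation, without a hypothesis test.

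The calls, the trained staff and the REDCap flag already exist. At about a minute per call, 800 participants × 2 calls × 1 minute = 1,600 minutes, or roughly 27 hours over the whole trial, plus one short form and one table. Fatigue counts will still partly reflect underlying illness, so the between-arm difference should be read rather than the absolute level.

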8.3.6 SERIOUS ADVERSE EVENT REPORTING

Not applicable.

8.3.7 REPORTING EVENTS TO PARTICIPANTS

Not applicable.

8.3.8 EVENTS OF SPECIAL INTEREST

Not applicable.

8.3.9 REPORTING OF PREGNANCY

Not applicable.

8.4 SUBJECT SAFETY

Any unexpected problem related to the Research that negatively affects the rights, safety or welfare of subjects and is not described as such in the materials describing risks associated with the study.

8.4.1 DEFINITION OF UNANTICIPATED PROBLEMS (UP)

Unanticipated problems are defined by DHHS 45 CFR part 46 as any incident, experience, or outcome that meets all of the following criteria:

- unexpected, in terms of nature, severity, or frequency, given (a) the research procedures that are described in the protocol-related documents, such as the IRB-approved research protocol and informed consent document; and (b) the characteristics of the study population;
- related or possibly related to participation in the research (in this guidance document, possibly related means there is a reasonable possibility that the incident, experience, or outcome may have been caused by the procedures involved in the research);
- suggests that the research places participants or others at a greater risk of harm (including physical, psychological, economic, or social harm) than was previously known or recognized.

It will be extremely unlikely in this study that the events of fatigue and emotional distress would meet the all of the criteria above.

8.4.2 UNANTICIPATED PROBLEM REPORTING

If we encounter any adverse event that meets the definition above and that is related to the intervention, the PI will notify the Emory IRB and NINR Program Official and the DSMB within 24 hours of the event being reported to the PI. The expedited report will be followed by a detailed, written SAE report as soon as possible.

8.4.3 REPORTING UNANTICIPATED PROBLEMS TO PARTICIPANTS

Not applicable.

9 STATISTICAL CONSIDERATIONS

9.1 STATISTICAL HYPOTHESES

- Primary Endpoint(s):
 - 1) The number of SPIRIT dyads who are congruent on goals of care at 2 weeks post-intervention will be significantly higher than that of control dyads.
 - 2) Patient decisional conflict scores at 2 weeks post-intervention will be significantly lower than those of control dyads.
 - 3) Surrogate decision making confidence (DMC) scores at 2 weeks post-intervention will be significantly higher than those of control dyads.

- 4) The number of SPIRIT dyads who are congruent on goals of care and confident surrogate (DMC=3 or higher) at 2 weeks post-intervention will be significantly higher than that of control dyads.
- Secondary Endpoint(s):
 - 1) HAD-anxiety scores in SPIRIT surrogates will be significantly lower than those of control surrogates at 3 months after the patient's death.
 - 2) HAD-depression scores in SPIRIT surrogates will be significantly lower than those of control surrogates at 3 months after the patient's death.
 - 3) PTSS-10 scores in SPIRIT surrogates will be significantly lower than those of control surrogates at 3 months after the patient's death.
- Exploratory: Among patients who have died,
 - 1) The percentage of patients hospitalized during the final month of life in the SPIRIT group will be significantly lower than that in the control group.
 - 2) The percentage of patients admitted to an ICU during the final month of life in the SPIRIT group will be significantly lower than that in the control group.
 - 3) The percentage of patients having intensive procedures during the final month of life in the SPIRIT group will be significantly lower than that in the control group.
 - 4) The length of hospital stay during the final month of life in the SPIRIT group will be significantly shorter than that in the control group.

For Supplement Aims:

- Aim 1:
 - 1) The number of SPIRIT dyads who are congruent on goals of care at 2-3 days post-intervention will be higher than that of control dyads.
 - 2) Patient decisional conflict scores at 2-3 days post-intervention will be lower than those of control dyads.
 - 3) Surrogate decision-making confidence (DMC) scores at 2-3 days post-intervention will be higher than those of control dyads.
 - 4) The number of SPIRIT dyads who are congruent on goals of care and confident surrogate (DMC=3 or higher) at 2-3 days post-intervention will be significantly higher than that of control dyads.
 - 5) The proportion of decisions made at 6 months (e.g. stopping dialysis, DNR order, and hospice enrollment etc.) follow-up or death of patient will be higher in the intervention dyads than that of control dyads.
- Aim 2:
 - 1) HAD-anxiety scores in SPIRIT surrogates will be lower than those of control surrogates at 1 month after the patient's death.
 - 2) HAD-depression scores in SPIRIT surrogates will be lower than those of control surrogates at 1 months after the patient's death.

Supplement cohort study:

Aim 1. Changes in patient's goals of care preferences over time (T2-T3 and T2-T4) in the intervention group will be smaller than those in the control group.

Aim 2. Changes in the preparedness outcomes over time in the intervention group will be smaller than those in the control group.

Aim 3. The COVID-19 Related Stress and race/ethnicity will be significantly associated with changes in goals of care stability and the preparedness outcomes.

